### 1.3 Rationale

High dose Interleukin-2 and nivolumab are both active agents in metastatic clear cell renal cell cancer with complementary and potentially synergistic mechanisms of action at distinct points of the T-lymphocyte activation, trafficking, proliferation and anti-tumor cell cytotoxicity process. PD-L1 expression on tumor cells is thought to be induced by infiltrating CD8+ T cells in the tumor microenvironment.

**We hypothesize** that concurrent PD-1 inhibition synergistically enhances the anti-tumor immune response to HD IL-2 in metastatic clear cell RCC. We postulate that the combination of the two therapies would result in an increase in the overall response rate, complete response rate, and improved survival outcomes compared to either of the individual therapies.

**We propose** a single arm, multi-site, phase Ib/II clinical trial of Nivolumab (480 mg/dose intravenously over 60 minutes every 28 days), a PD-1 inhibitor, in combination with standard doses of High Dose Interleukin-2 (600,000 IU/kg/dose intravenously) every 8 hours for up to a maximum of 28 doses during two 5-day cycles one week apart in interleukin-2 eligible clear cell mRCC subjects.

#### **1.4 Correlative Studies**

- 1) We propose to descriptively profile the circulating T-cell repertoire by performing Flow Cytometry and cell sorting in whole blood samples at the time points listed in Section 6.4 Time and Events Table. These studies will be hypothesis generating and could possibly guide timing and combination of immunotherapies in renal cell cancer.
- 2) We will archive patient tumor and serum samples for future testing including but not limited to PD-L1 testing and anti-drug antibody testing.

### **2.0 STUDY OBJECTIVES**

#### **Phase Ib portion:**

##### **2.1 Primary Objective**

- 2.1.1 To estimate the safety and toxicities of High Dose Interleukin-2 in combination with the immune checkpoint inhibitor Nivolumab in metastatic clear cell renal cell carcinoma

#### **Phase II portion:**

##### **2.2 Primary Objective**

- 2.3.1 To assess the efficacy of High Dose Interlukin-2 in combination with the immune checkpoint inhibitor Nivolumab in metastatic clear cell renal cell carcinoma.

##### **2.3 Secondary Objectives**

- 2.4.1 To determine the safety of High Dose Interlukin-2 in combination with the immune checkpoint inhibitor Nivolumab in metastatic clear cell renal cell carcinoma.
- 2.4.2 To profile circulating T cell repertoire by flow cytometry before and during therapy.

##### **2.4 Exploratory Objectives**

- 2.5.1 To bank tissue and serum specimens for future correlative analyses and anti-drug antibody testing.

#### **Study Endpoints**

##### **Phase Ib portion:**

Primary Endpoint: To establish that the combination of High Dose Interlukin-2 and Nivolumab is safe and tolerable by monitoring 10 patients for immune mediated grade 3/4 events of interest for 28 days from the first dose of Nivolumab.

##### **Phase II portion:**

Primary Endpoint: Efficacy of the combination therapy will be determined by the overall response (ORR) rate/proportion with response including complete response rate/proportion as assessed by RECIST 1.1 criteria.

Secondary Endpoints:

Safety will be defined by the frequency of protocol specified therapy-related grade 3-5 adverse events including events of clinical interest for duration of protocol specified therapy and an additional 60 days beyond that, as assessed by NCI's CTCAE version 4.0.

Survival endpoints for efficacy are 24-month Overall Survival (OS) and 24-month Progression-Free Survival (PFS) in subjects treated with the combination by RECIST 1.1 criteria.

To descriptively characterize the circulating immune cell repertoire before and after start of combination therapy with High Dose Interlukin-2 in combination with the immune checkpoint inhibitor Nivolumab

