
Study Duration	
24 months of accrual
 
24 months of follow-up (counting from week 1)

Study Center(s)	
4 Sites including lead site: University of Michigan.

Objectives	
Phase Ib:
 
Primary Objective:
 
 
1. To estimate the safety and toxicities of High Dose Interleukin-2 in combination with the immune checkpoint inhibitor Nivolumab in metastatic clear cell renal cell carcinoma.
 
 
Phase II:
 
Primary Objective:
 
 
1. To estimate the efficacy of High Dose Interleukin-2 in combination with the immune checkpoint inhibitor Nivolumab in metastatic clear cell renal cell carcinoma.
 
 
Secondary Objectives:
 
 
1. To determine the safety of High Dose Interleukin-2 in combination with Nivolumab in metastatic clear cell renal cell carcinoma.
 
2. To profile circulating T cell repertoire by flow cytometry before and during therapy.
 
 
Exploratory Objectives:
 
 
1. To bank tissue and serum specimens for correlative analyses and anti-drug antibody testing in the future.
 

Number of Subjects	
Number of evaluable subjects (those who receive at least 1 dose of HD IL2 and at least 1 dose of nivolumab) = 23. Subjects in the Phase 1b portion will be included in the overall toxicity and efficacy analysis of the study. Subjects who are not evaluable will be replaced. Up to 28 patients may need to be registered (enrolled) in order to obtain the 23 evaluable patients.

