## 5.0 TREATMENT PLAN

### 5.1 Treatment Dosage and Administration

Protocol treatment must start within 14 business days of enrollment to the study. The interleukin-2 (Proleukin) and Nivolumab (Opdivo) will be stored and prepared as described in the approved labels.

- 5.1.1 Therapy will start with high dose interleukin-2 (HD IL2) on week1 (day 1-5) and again on week 3 (day 1-5). Nivolumab will start on week 2 (optimally day 1 but can be given up to 3 weeks after IL-2 start but NOT be on the same week as any HD IL2 cycle) and continue every 4 weeks for up to 48 weeks on study unless one of the dose delay or stopping rules apply.
- 5.1.2 HD IL-2 will be administered in standard fashion at a fixed dose of 600,000 IU/kg/dose every 8 hours for a total of up to 14 doses (considered as one cycle) over 5 consecutive days (D1-D5), followed by a 9-day break and then another cycle at the same dose over another 5 consecutive days (D15-D19). Each HD IL-2 course consists of two cycles of up to 14 doses each separated by 9 days of rest.

Monitoring, supportive care measures for HD IL2 will be per institutional guidelines. The standard current guidelines for HD IL-2 administration based on Schwartzenruber et al. have proven to be safe at the participating institutions in the study over the years and will be used for this protocol.

Pre-medications and concurrent medications: Per institutional guidelines at each site usually include anti-emetics, anti-histamines, antipyretics/anti-inflammatory agents, anti-motility/anti-diarrheal agents, proton pump inhibitors, vasopressors as needed, medications for rigors as needed, hydration including boluses and maintenance fluids. It is recommended but not mandated that subjects be given anti-emetics for as needed (prn) use after each IL-2 therapy week to treat residual nausea. Furosemide (a loop diuretic) may also be given per treating investigator's discretion following each IL2 week. Please see IL-2 guidance document for more details.

Subjects will undergo placement of a central venous catheter before each course or cycle of therapy per institutional preferences.

NOTE: If the treating investigator determines another course of HD IL-2 beyond the 2 cycles after week 12 of protocol therapy specified in the protocol are in the

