### Dosing delays:

- **DURING IL-2 weeks**
  - Individual doses of IL-2 within each cycle may be skipped by the treating investigator at his or her discretion. Skipped doses will not be made up.
  
- **AFTER IL-2, BEFORE NIVOLUMAB**
  - All toxicities (with the exception of fatigue) attributed to IL-2 administration should have resolved or recovered to grade 1 or resolved or to baseline prior to starting nivolumab
  - Fatigue should have recovered to grade 2 or better
  - If toxicities have not improved to the levels listed above, nivolumab and the 2nd cycle of IL-2 should be held until toxicities improve to the above levels
  - If nivolumab or IL-2 is delayed >6 weeks as a result of a toxicity, the subject must be permanently discontinued from study therapy with the following exception:
    - If a steroid taper (to manage drug-related adverse events) is the reason for treatment delay of >6 weeks, and the subject's adverse events recover to grade 1 or better, continuation on study could be possible if approved by the principal investigator
  
- **AFTER NIVOLUMAB, PRIOR TO 2nd IL-2 CYCLE**
  - All immune mediated toxicities should have recovered to grade 1 or better prior to starting the second dose of IL-2 and subjects should be off systemic steroids or on a dose of ≤ prednisone 10mg (or equivalent alternative steroid).
  - Fatigue should have recovered to grade 2 or better
  - If specific toxicities are of unclear attribution (including for example: diarrhea, increased LFTs, cardiovascular disorders, mental status changes, pulmonary disorders and rash) they should be treated as possibly related to nivolumab and treated as per the tables in section 5.2.2. These toxicities must improve to grade 1 or better prior to proceeding with the second week of IL-2 therapy.
  - If toxicities have not improved to the levels listed above, nivolumab and the 2nd cycle of IL-2 should be held until toxicities improve to the above levels

- If nivolumab or IL-2 is delayed >6 weeks as a result of a toxicity, the subject must be permanently discontinued from study therapy with the following exception
  - If a steroid taper (to manage drug-related adverse events) is the reason for treatment delay >6 weeks, and the subject's adverse events recover to grade 1 or better, continuation on study could be possible if approved by the principal investigator
  
- **DURING NIVOLUMAB ONLY TIME PERIOD:**

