**7.1.6 Progression-Free Survival**

Progression-free survival (PFS) is defined as the duration of time from start of treatment to time of progression.

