## 11.2 Data Analyses Plans

Primary Endpoint Analysis:

Phase 1b: DLT count and proportion will be reported. Type, grade and attribution will be described by body system in the first 10 DLT evaluable patients. Number of IL-2 cycles and doses and Nivolumab doses will be summarized.

Phase II: Overall response rate at 12 weeks will be reported with the sample size and proportion of evaluable patients and the corresponding 95% exact binomial confidence interval.

Secondary Endpoint Analyses:

Safety will be defined by frequency of drug-related grade 3-5 adverse events including adverse events of interest within the duration of protocol, specified therapy and an additional 60 days following the last dose with the combination of HD IL2 and nivolumab, as assessed by NCI's CTCAE version 4.0. Counts and frequencies will be reported by body system, type and grade. Cycles and of each drug and doses/cycle of IL-2 will be described using descriptive statistics.

Survival endpoints are 24-month Overall Survival (OS) and 24-month Progression-Free Survival (PFS) as assessed by RECIST 1.1 criteria in subjects treated with the combination. Product-limit estimates from Kaplan-Meier methods will be used to report the 24-month OS and PFS proportions with 95% confidence intervals. Kaplan-Meier figures will be produced.

Interim Analysis for efficacy: An interim analysis for efficacy is planned after 12 response evaluable patients have been enrolled (total in the phase I b/II portions). If 2 or less patients have a response at 12 weeks then the trial will terminate. .

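### 24-month OS and PFS appear to be restricted to patients who reached nivolumab yet timed from IL-2 day 1, which would bias OS, and less strictly PFS, upward

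*Combined protocol and SAP*

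**What the plan says.** - **Set.** Study Endpoints (Phase II) names the survival population: "Survival endpoints for efficacy are 24-month Overall Survival (OS) and 24-month Progression-Free Survival (PFS) in subjects treated with the combination by RECIST 1.1 criteria". Section 11.2 repeats it: "as assessed by RECIST 1.1 criteria in subjects treated with the combination". Neither place defines the phrase.
- **Nearest definition.** The synopsis gives: "Number of evaluable subjects (those who receive at least 1 dose of HD IL2 and at least 1 dose of nivolumab) = 23". Section 5.9 replaces anyone who falls short of this, and the synopsis allows up to 28 registrations to reach 23.
- **PFS clock.** Section 7.1.6: "Progression-free survival (PFS) is defined as the duration of time from start of treatment to time of progression". Section 5.1.1 starts therapy with IL-2 in week 1.
- **OS clock.** No origin is stated. The synopsis and section 5.7 count follow-up from week 1.
- **Gap.** Nivolumab follows one to three weeks after IL-2 starts (5.1.1, 5.1.3). For the first three patients it comes in the week after the second IL-2 cycle, so about three weeks (5.1.4). Under section 5.2 (Dosing delays) it can come later: "If toxicities have not improved to the levels listed above, nivolumab and the 2 nd cycle of IL-2 should be held until toxicities improve". A toxicity delay beyond six weeks ends study therapy, apart from a steroid-taper exception.
- **Method.** Section 11.2: "Product-limit estimates from Kaplan-Meier methods will be used to report the 24-month OS and PFS proportions with 95% confidence intervals". No delayed entry, landmark or all-treated analysis is given.

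**The concern.** If membership of the survival set depends on a first nivolumab dose but time runs from IL-2 day 1, entry depends on something that happens after the clock starts. A patient who begins IL-2 and dies, deteriorates or stops for toxicity before nivolumab leaves no trace in the Kaplan-Meier curve and is replaced. Every patient who does enter is counted as at risk from week 1, during weeks in which, for OS, that patient could not have died.

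The effect would be to flatter the early part of the curve and the 24-month estimate. This matters because section 1.3 hypothesises better survival than with either drug alone, and the synopsis names the two monotherapies as reference therapy. With no control arm, readers are likely to set these estimates beside the survival results quoted in section 1.2.

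**Working it through.** **The plan's own figure.** The documents give no figure for 24-month OS or PFS. The only number carried into this check is 23 evaluable patients, from the Simon design in section 11.1 (stop at 2 or fewer of 12; positive if more than 8 of 23; 25% versus 46%). An exact two-stage binomial calculation gives type I error 0.0944, power 0.8012, and early stopping 0.3907 at 25% and 0.0363 at 46%. The stated 10%, 80%, 39% and 3.6% hold, and a minimax search returns the same design.

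**Inputs for illustration.** Median OS 25 months (nivolumab) and 42.8 months (high-dose IL-2), and median PFS 4.6 months (nivolumab), all from section 1.2. Constant hazard is my assumption. The gap is 1 or 3 weeks as planned, and 3 + 6 = 9 weeks with the longest ordinary toxicity delay.

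**Step 1: guaranteed time alone.** With median m and gap g in months (weeks × 7 / 30.4375), all treated patients have S(24) = 0.5^(24/m). Patients selected for surviving the gap, but timed from IL-2 day 1, show S(24)/S(g), where S(g) = 0.5^(g/m). Example for OS with m = 25 and a 3-week gap: S(24) = 0.5^0.96 = 0.5141, g = 0.690, S(g) = 0.9811, and 0.5141/0.9811 = 0.5240.

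| Endpoint, median | All treated | 1 week | 3 weeks | 9 weeks |
|---|---|---|---|---|
| OS, 25 months | 51.4% | 51.7% (+0.3) | 52.4% (+1.0) | 54.4% (+3.0) |
| OS, 42.8 months | 67.8% | +0.3 | +0.8 | +2.3 |
| PFS, 4.6 months | 2.7% | +0.1 | +0.3 | +1.0 |

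**Step 2: exclusion of early failures.** Suppose k patients start IL-2, never receive nivolumab, and do not survive 24 months. The all-treated estimate is the reported one times 23/(23 + k). The registration ceiling gives at most 28 − 23 = 5 non-evaluable patients; how many of these start IL-2 is unknown.

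- k = 0: 51.4%, no difference
- k = 1: 23 × 0.514/24 = 49.3%
- k = 3: 23 × 0.514/26 = 45.5%
- k = 5: 23 × 0.514/28 = 42.2%

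If the excluded patients have half the survival of the others, the all-treated figure is 50.3% (k = 1) to 46.8% (k = 5). If they survive equally well, there is no difference. For PFS at 2.7%, k = 5 gives 2.2%, about half a point.

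The two steps should not be added together. Deaths in the gap are among the k patients, so Step 1 is the part of Step 2 that arises from gap deaths at the assumed hazard.

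**The case against.** The strongest reply is that the flawed analysis is inferred. Section 11.1 ties the rule of one dose of each drug to response and DLT evaluability, and nothing applies it to survival by name. In section 11.2 the safety endpoint also mentions the combination, although sections 5.2, 7.1.1 and 7.2 count anyone who received study drug; the phrase may simply name the regimen. The OS origin is likewise inferred from the follow-up clock. This stands as a limit on certainty. It does not remove the problem, because the phrase read plainly produces the mismatch and no text rules it out.

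A reader might also infer that neither a death nor a progression can occur before nivolumab by construction. For OS counted from week 1 that follows from the reading above. For PFS the documents do not support it:

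- The first scheduled scan is at week 12 (6.2.2), so progression would rarely be recorded in the gap for any patient.
- Footnote 6 of the Time and Events Table ends nivolumab at progression with no clinical benefit, whereas section 5.5 ends therapy at progression. Those passages need reconciling; as they stand, progression does not clearly bar entry.
- Section 7.1.6 does not name death as an event.

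Finally, the effect may be small. Section 1.2 puts IL-2 mortality below 1% in recent trials, the 28 is a ceiling that may include patients never dosed, and stopping for toxicity is not itself an OS or PFS event. With 23 patients and 51.4% survival, ignoring censoring, the 95% half-width is about 1.96 × √(0.514 × 0.486/23) = 0.20, or 20 points. All of this stands. It bears on size and leaves the direction unchanged whenever the excluded patients do worse.

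**Conclusion.** The point holds in a limited form. On the most natural reading of the survival set, with time from week 1, 24-month OS is biased upward relative to all patients who start treatment; PFS is biased in the same direction but less strictly. Both the set and the OS origin are gaps in the definitions, so this is a conclusion about the likely analysis rather than a stated one.

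The size is not fixed by the documents. On planned timing, guaranteed time is worth about 0.3 to 1.0 points of OS. It becomes material only with long delays or if several IL-2-treated patients fail before nivolumab. It would be tempting to quote the 9-point gap at k = 5 as the size of the immortal-time bias. The documents do not support that: it is a denominator effect that requires all five non-evaluable patients to have started IL-2 and none to survive 24 months.

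These endpoints are secondary and descriptive, with no test or planned comparison. The ORR decision rule is unaffected.

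**What to change.** In Study Endpoints and section 11.2, state that 24-month OS and PFS are estimated from the first IL-2 dose in all patients who receive at least one dose of protocol therapy. This settles the analysis set and the OS origin together. If the combination-treated subset is also shown, start its clock at the first nivolumab dose, or use delayed entry at that date in the product-limit estimate. Report how many treated patients never reached nivolumab, and why.

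The cost is about two sentences and a slightly less favourable estimate. OS needs no new data, because sections 5.6, 5.7 and 6.3 already require follow-up after treatment stops. PFS is less clean: section 6.3 leaves scans after therapy to the treating investigator, so the few added patients would rely on standard-of-care imaging, and the report should say so.

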**3.0 PATIENT ELIGIBILITY**

Subjects must meet all of the inclusion and exclusion criteria to be enrolled to the study. Study treatment may not begin until a subject is enrolled.

**3.1 Inclusion Criteria**

- 3.1.1 Subjects must have a histologic diagnosis of clear cell renal cell carcinoma (pure or mixed) with radiologic or histologic or cytologic evidence of metastatic disease.
- 3.1.2 Subjects may have received up to 2 prior lines of systemic therapy (excluding any neoadjuvant/adjuvant therapy) including anti-VEGF or VEGFR inhibitor (e.g. sorafenib, pazopanib, sunitinib, bevacizumab, axitinib) or mTOR inhibitor (e.g. everolimus or temsirolimus) for metastatic disease.
- 3.1.3 Age  $\geq$  18 years at the time of consent.
- 3.1.4 ECOG performance status of 0 or 1.
- 3.1.5 Adequate organ and marrow function as defined below:

White blood count	$\geq 3000/\text{mm}^3$
Platelet count	$\geq 100,000/\text{mm}^3$
Hemoglobin	$\geq 10.0 \text{ g/dl}$
ALT, AST	$\leq 2.5x$ upper limit of institutional normal reference range
Total Bilirubin	$\leq 1.5x$ the upper limit of normal (patients with confirmed Gilbert's syndrome (persistent or recurrent hyperbilirubinemia in the absence of evidence of hemolysis or hepatic pathology) will be allowed to enroll after discussion with the principal investigator if total bilirubin is $\leq 3x$ the upper limit of normal),
Serum creatinine	$\leq 1.5x$ laboratory upper limit of normal or calculated creatinine clearance of $\geq 50\text{ml/min}/1.73 \text{ m}^2$ )
PT/INR	$\leq 1.5$
Urine	$\leq 1$

Protein/Creatinine ratio	
--------------------------	--

- 3.1.6 Women of childbearing potential must have a negative serum or urine pregnancy test within 28 days prior to registration. Women of non-childbearing potential are defined as those who have no uterus, ligation of the fallopian tubes, or permanent cessation of ovarian function due to ovarian failure or surgical removal of the ovaries. All others are considered women of child bearing potential.
- 3.1.7 Females and males of childbearing potential must be willing to use an effective method of contraception (hormonal or barrier method of birth control; abstinence) from the time consent is signed until 12 weeks (for males) and 5 months (for females) after treatment discontinuation.
- 3.1.8 Subjects must have measurable disease on physical exam or imaging per RECIST 1.1 criteria.
- 3.1.9 An archived tissue block with the subject's renal cell carcinoma must be identified prior to registration. Please see Section 10.0 for additional information
- 3.1.10 Subjects must be considered appropriate candidates for HD IL-2 by one of the treating investigators listed on the protocol. HD IL-2 candidacy evaluation is per institutional guidelines at each site and should include a dobutamine stress echocardiogram or equivalent. Subjects with a positive stress test for cardiac ischemia would be excluded from this trial.
- 3.1.11 No clinically significant infections or any other medical condition(s) that render the subject ineligible for high dose IL-2 therapy as judged by the treating investigator.
- 3.1.12 Ability to understand and the willingness to sign a written informed consent.

**3.2 Exclusion Criteria**

- 3.2.1 Prior interferon or interleukin-2 therapy is NOT allowed.
- 3.2.2 Prior anti-PD-1/PD-L1 targeted therapy is NOT allowed. Prior CTLA-4 therapy or CD40/CD40L targeted therapy is allowed.
- 3.2.3 Prior systemic treatment must be completed at least 14 calendar days prior to registration and the subject must have recovered from the toxicities of treatment to grade 1 or better.
- 3.2.4 Prior radiation therapy is allowed if completed at least 14 calendar days prior to registration.
- 3.2.5 Treatment with any investigational agent or on an interventional clinical trial within 30 days prior to registration.
- 3.2.6 No prior or concurrent malignancy is allowed except for: adequately treated basal cell or squamous cell skin cancer, in situ cervical cancer, localized or locally advanced prostate cancer definitively treated without recurrence or with

biochemical recurrence only, or any other cancer fully treated or from which the subject has been disease-free for at least 2 years.

- 3.2.7 Current untreated brain metastasi(e)s. If treated history of CNS metastases, should have completed radiation or surgery at least 12 weeks prior and off systemic corticosteroids.
- 3.2.8 Autoimmune diseases such as rheumatoid arthritis are NOT allowed. Vitiligo, mild psoriasis (topical therapy only) or hypothyroidism are allowed
- 3.2.9 Medical need for systemic corticosteroids >10mg prednisone daily or equivalent alternative steroid (except physiologic dose for adrenal replacement therapy) or other immunosuppressive agents (such as cyclosporine or methotrexate) Topical and inhaled corticosteroids are allowed if medically needed
- 3.2.10 History of allergic reaction to interleukin-2 or nivolumab
- 3.2.11 Prior history of psychiatric disorder or seizure disorders which could be exacerbated by Interleukin-2 as judged by the treating investigator.
- 3.2.12 Evidence of significant cardiovascular disease including history of recent (< 6 months prior) myocardial infarction, congestive heart failure, primary cardiac arrhythmias (not due to electrolyte disorder or drug toxicity, for example) beyond occasional PVC's, angina, positive low-level stress test, or cerebrovascular accident. All patients should have baseline pulmonary function tests. Adequate pulmonary function should be documented (FEV1 >2 liters or ≥75% of predicted for height and age) prior to initiating therapy.
- 3.2.13 Any history of HIV or hepatitis B infection
- 3.2.14 Any other medical or surgical condition or disease that, in the judgment of the treating physician, renders subject ineligible for High Dose Interleukin-2 therapy.
- 3.2.15 Any history of organ allografts
- 3.2.16 Any history of cerebrovascular accident or transient ischemic attack

